3.0 Objectives/Aims

Aim 1: To test the feasibility (compliance and effectiveness) of cognitive-motor exergaming (CogXergaming) in the frail older adults and to compare the improvements in behavioral biomarkers in this group across balance, muscle fitness, cardiovascular fitness and global cognition to the group receiving the Matter of Balance training.

Hypothesis: Participants will respond well to CogXergaming training paradigm and demonstrate significant improvements in balance, muscular fitness, cardiovascular fitness and global cognition as compared to the Matter of Balance training group.

Aim 2: To examine the effect of CogXergaming on physical activity levels and quality of life measures post-intervention.

Hypothesis: The participants who received CogXergaming will demonstrate significant improvement in physical activity and quality of life post-training as compared to their own pre-training scores.

Aim 3: To examine the effect of CogXergaming structural and functional connectivity within the cognitive-motor areas pre and post training to establish effect size.

Hypothesis: Post-training, participants will demonstrate improved memory consolidation, attention, motor planning and execution compared to pre-training indicating improved functional connectivity within the cognitive-motor areas.

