6.0 Study Design and Procedures

- This study will be a randomized controlled design.
- During the telephone screening, all the participants will be asked to choose a group that
 they prefer to participate which includes 3 options: Group 1: In-person assessments
 and in-person training; Group 2-In-person assessments and online training and Group
 3- Online assessments and online training.

[figure not shown]

- Figure 1 above shows recruitment and distribution of participants into differenct groups based on the options given for assessment and training to the participants during telephone screening.
- After the participants are allocated to groups 1,2 and 3 depending on their choice, each
 participant from every group will be randomly assigned either Group A (CogXergaming)
 or Group B (Matter of balance) for training by flipping a coin.
- Al the participants will be undergo 1-on-1 testing and training.
- Study protocol will vary according to the groups that the participants choose to be in (Groups 1,2 or 3).
- For Group 1 (In-person assessments and in-person training): Group A (CoXergaming) will undergo a total of 8 weeks session with first week and last week comprising of assessment. 6-week training will be delivered using the Nintendo Wii-Fit gaming system and a pointer mouse. Participants will visit the laboratory 3 times a week for 6 weeks with each session lasting for 60 minutes (18 training sessions). During training session, participants will wear a gait belt and will be guarded by a research assistant for safety. On the other hand, if the Group 1 participant gets assigned to Group B (Matter of balance) then participants from Group B will undergo a total of 10 weeks session with first week and last week comprising of assessment. The participants will undergo an 8-week (one session a week for 2 hours/day, 8 sessions in total) structured intervention specifically designed to reduce the fear of falling and to increase the engagement in PA.

| Test | Pre- test | CogXergaming/TeleXercise Intervention (6 weeks) | | | | | | | | | | | Post-test | | | | | | | |
|---------|--------------|---|---|---|---|---|---|---|---|---|----|----|-----------|----|----|----|----|----|----|-----|
| Session | 1-4 | 1 | 2 | 3 | 4 | 5 | 6 | 7 | 8 | 9 | 10 | 11 | 12 | 13 | 14 | 15 | 16 | 17 | 18 | 1-3 |
| Week | 1 | 2 | | 3 | | 4 | | 5 | | 6 | | | 7 | | | 8 | | | | |

| Test | Pre-test | M | latte | Post-test | | | | | | |

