6.1 Participant Screening

Inclusion Criteria

- Walking speed <0.8m/s
- Self-reported Physical activity <3 hours/week
- Hand grip strength <30 kgs for men & <20 kgs for women (this will be assessed only for participants who come for in-person assessment)
- Not on any sedative drugs
- Can understand & communicate in English
- Ability to walk more than 30 feet with or without an assistive device
- Must have either a desktop computer/laptop/tablet with access to internet (only for participants who choose to go for online assessments and/or training)Must have a helper buddy assistance (only for participants who choose to go for online assessments and/or training). The helper buddy will be asked to stay in the same room throughout the online assessment and online training sessions. The helper buddy will not participate in any other way throughout the research procedures. In case of any adverse event, we will follow the adverse event protocol. The session will be immediately concluded, and the participant will be provided all the necessary support by the helper buddy while the research personnel stays online to ensure the participant is taken care of. The participant will be asked for symptoms and the type of discomfort he/she is experiencing. The adverse event will be immediately reported to the PI and the participant will be asked to visit his physician or doctor to seek medical attention in case the symptoms persist for more than a day. In case of emergency, like chest discomfort, the helper buddy will be asked to call 911 immediately
- 2-minute step in place test or walk around: The participant is asked to stand up straight next to the wall with the heart rate/O2 monitor plugged in to the index finger. The subject then marches in place or walks around the room (with health coach able to see them on the screen) for two minutes. On completion, the health coach will obtain the heart rate and oxygen saturation. If the HR exceeds 85% of age appropriate HR max and O2 saturation falls below 90% then they will be excluded from the study.

Exclusion Criteria

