6.2 Intervention

Group A – CogXergaming

[For Group 1(in-person assessments and in-person training)]

CogXergaming based cognitive-motor balance training will be delivered to group A using the commercially available Wii-Fit Nintendo and a mouse in conjunction with cognitive training. All participants will undergo 18 sessions of training in a tapering manner for six weeks with 60-90 minutes of training per session, i.e., 3 sessions each week till the 6th week. Each session will be divided into 3 sub-sessions, where each sub-session will consist of playing 4 to 6 games in conjunction with cognitive task. All the games will be performed using a Wii-Fit balance board in front of a TV screen. At the beginning of each session, 10 minutes of warm exercises will be provided that includes self-stretches, lunges, squats, high stepping and chair rises. The participant

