
Group A – CogXergaming in the form of TeleXercise intervention
[For Group 2 (in-person assessments and online training) & Group 3 (online assessments and online training)]

The TeleXercise intervention proposes to deliver exercises via exergaming-based animation videos combined with or without explicit cognitive exercises delivered by a research personnel monitoring the intervention. All the online training sessions will be carried out on one-on-one basis. Participants will need a desktop computer/tablet or smart phone of their own with access to internet on which the commercially available application will be installed. Research personnel will set up meeting invites and send them links via their preferred receiving mode (SMS or email). Once the research personnel admits all participants into the room via the secure link the research personnel will start the intervention. The research personnel will launch the Mimic-Game-&-Groove application on their computer and share their screen with the participants. Participants have to turn their videos on for the research personnel to see them. The audio will be kept in mute by the health coach and once the participant tries to talk or show any discomfort he/she will unmute in any unanticipated event. The intervention consists of participants mimicking the exercises that are shown in form of games and dances on their screen (similar to exergaming but being passive rather than interactive). The participants will not receive knowledge of performance or knowledge of results like in traditional exergaming; however, after each session, they will receive a brief feedback by the health coach, 1) qualitative based on the movements, 2) quantitative based on their heart rate max (intensity achieved) and the number of steps per session (measured via wearable sensors/smartphone). Participants will receive the TeleXercise intervention for three times per week for 6 weeks (18 sessions) with each session lasting about 1 hour and 30 minutes, including warm-ups, rests, and a cooldown. Training will consist of 20 minutes of warm-up -joint mobility, walking, and stretching exercises of moderate intensity, and cool-down- low-intensity stretching exercises and 1 hour of TeleXercise. A wearable device provided will measure the heart rate and physical activity during the course of training. They will be asked to read out the Heart rate and number of steps before the training begins (which will be displayed on the wearable device). Furthermore, after each set of exercise, they will be asked to note down their heart rate and number of steps displayed on their watch and when asked they should report it to the research personnel. Participants must be below 85% of the age predicted maximum heart rate to continue testing and training. All participants will be provided with a feasibility questionnaire and their compliance will be recorded at the end of the 4 weeks of training. Participants are provided with a set of balance exercises, which are demonstrated via animated avatars. The balance exercises includes non-interactive balance games (stepping forward, backward, sideways), Tai-Chi, Weight shifting (to right leg, left leg and practice distributing equal weights on both the legs), Aerobic (stepping in place), dance, strength, and stretching. Please see the figure below

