6.4 Outcomes

Assessment: The following tests will be administered as baseline and post-intervention. Table 1: Assessment variables for Groups 1 and 2 (In-person assessment) and Group 3 (Online-assessment)

| Group 1 and 2 Assessments (In-person assessment) | Group 3 Assessments (Online Assessment) | | | | | | |
|--|---|--|--|--|--|--|--|
| Balance Intentional balance control (Limits of stability test) (single and Dual task conditions) Postural control (sensory organization test) (single and Dual task conditions) Reactive balance control (Stance perturbation test) (single and Dual task conditions) NIH balance Toolbox (Standing balance test) Gait GaitRite mat (single and Dual task conditions) NIH Balance toolbox (4m walk Gait speed test) | Balance - 30-second chair stand test - Four-step square test - Sharpened Romberg's - One leg stance test Gait - Tinetti Performance Oriented Mobility Assessment | | | | | | |
| Muscular fitness - Isokinetic Dynamometer - B-mode Ultrasonography Cardiovascular fitness - Heart rate variability - YMCA submaximal cycle Ergometer test - NIH Balance toolbox (2-minute walk endurance test) | Cardiovascular fitness - 2-minute step in place test | | | | | | |
| Cognitive performance - Neuropsychological battery tests - NIH cognitive toolbox - Auditory clock test and letter number sequencing (single and Dual task conditions) Physical activity and motivation - Smartphone (Android/iphone) | Cognitive performance - Neuropsychological battery tests - NIH cognitive toolbox - Auditory clock test and letter number sequencing (single and Dual task conditions) Physical activity and motivation - Smartphone (Android/iphone) | | | | | | |

| fMRI scanning | - |
|---|---|
| - Intrinsic motivational index | - Intrinsic motivational index |
| - Physical activity scale for the elderly | - Physical activity scale for the elderly |
| - Quality of life (SF-36) | - Quality of life (SF-36) |
| - Wearable sensor | - Wearable sensor |
| | |

Aim 1: Balance and Gait tests:

Balance:

For In-Person Assessment (Group 1 and 2)

Intentional balance control

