Questionnaires such as **Physical Activity Scale for elderly** will be self-reported by the participant. Also, number of steps per session will be assessed using participants smartphone. For participants who have iPhones with IOS platform we shall use the "Health" application, and data will be retrieved in excel format by the use of "Qs access" application. For participants with Android phones, the "Google Fit" application will be downloaded on the phone, and data retrieved in excel format from participants' google account through the website "https://takeout.google.com/". Participants will be educated on how to email their data. Participants will be provided with a step-by-step upload

information sheet for iPhone and Android and be guided by the remote research personnel if needed any further help. All these applications are free of charge to participants and researchers. Additionally, a wearable sensor (Fitbit) would be mailed to them to their address and the physical activity (# of steps) will be recorded during the training sessions.

The Fitbit Sensor can track steps (walking & running), distance (km & miles), calories burned, exercise time and heart rate. It also stores up to 30 days of daily activity records. There is no risk involved in using Fitbit sensor as a physical activity monitor. Once they receive the sensor, they would be asked to wear it around their wrist and charge the sensor as required. After the completion of the study they would be required to mail back the sensor provided to them. A self-addressed stamped envelope will be provided to the participants to accomplish sending the same

Quality of Life: This will be assessed using the SF-36 questionnaires. Social community interactions will be assessed by the Community Integration questionnaires, The Physical Activity Scale for the Elderly will assess self-reported engagement in PA and the Geriatric Depression Scale will assess depression levels.

Motivation – Motivation index found to correlate highly with compliance will be evaluated by the 37 item self-report Intrinsic Motivational Inventory (Measures participants' Interest/Enjoyment of a target activity, and their Perceived-Competence, - Effort, and the activity's Value/Usefulness. These measures will be obtained after the intervention is completed.

AIM 3: Magnetic Resonance Imaging (MRI):

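### The post-test activity scale does not exclude the trial's own training sessions, so arm A's self-reported gain in Aim 2 could come from attendance alone

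*Combined protocol and SAP*

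**What the plan says.** Section 3.0, Aim 2, predicts that participants who received CogXergaming "will demonstrate significant improvement in physical activity and quality of life post-training as compared to their own pre-training scores". That is a before-after comparison within arm A.

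Section 6.4 introduces its outcome table with "The following tests will be administered as baseline and post-intervention". The table lists the Physical Activity Scale for the Elderly for all three delivery groups, and the text adds that "The Physical Activity Scale for the Elderly will assess self-reported engagement in PA". Section 6.4 also tracks weekly steps before and after the intervention, and separately records steps during training sessions.

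Section 6.0 gives the in-person CogXergaming arm a "total of 8 weeks session with first week and last week comprising of assessment". Its schedule table, which also covers the online version, puts training in weeks 2 to 7 and the post-test in week 8. Arm B trains in weeks 2 to 9 and is tested in week 10.

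For session length, section 6.0 gives 60 minutes three times a week in person. Section 6.2 describes the same in-person programme "with 60-90 minutes of training per session" and the online version "with each session lasting about 1 hour and 30 minutes, including warm-ups, rests, and a cooldown". Arm B has one 2-hour session a week.

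Entry under section 6.1 requires "Self-reported Physical activity <3 hours/week".

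The documents do not give the scale's recall window, the day in the post-test week on which it is completed, or whether study sessions count.

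**The concern.** A questionnaire about recent activity, completed in the week after training stops, can look back into the training period. The same questionnaire at baseline cannot. Unless participants are told otherwise, some will report supervised study sessions as physical activity, and the change score will then contain the intervention itself.

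Aim 2 is exposed because it compares arm A with its own earlier scores, so no control arm absorbs the artefact. The background in section 2.0 motivates the trial by the limited lasting behaviour change seen after earlier activity programmes. A rise that consists of attendance would not answer that question, and it would feed an inflated effect into the larger trial that section 12.0 says this pilot will inform. Once the answers are collected without an instruction, analysts cannot separate the two kinds of activity.

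**Working it through.** **Inputs from the documents.** Arm A: 3 sessions a week for 6 weeks; 60 min (6.0), 60 to 90 min (6.2, in person) or about 90 min (6.2, online). In-person breakdown in 6.2: 10 min warm-up, 30 min exergaming, 20 min break. Online breakdown in 6.2: 20 min warm-up and cool-down, 60 min TeleXercise. Arm B: 1 × 2 h a week. Entry limit: under 3 h/week. Analysed sample in 12.0: 16 per subgroup.

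**Plan's own figures.** 3 × 6 = 18 sessions and 10 + 30 + 20 = 60 min; both agree with the text. 120 × (1 − 0.20) = 96 and 96 / 6 = 16; these agree too.

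**Weekly load in arm A.**
- Scheduled: 3 × 60 min = 3.0 h; 3 × 90 min = 4.5 h.
- Active, in person: 3 × (10 + 30) min = 3 × 40 min = 2.0 h.
- Active, online: 3 × (20 + 60) min = 3 × 80 min = 4.0 h.

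**Overlap with the questionnaire.** Assumptions: sessions fall on days 1, 3 and 5 of each training week, and the recall window is the 7, 14 or 28 days before completion. Number of sessions inside the window:

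| Day of week 8 | 7-day | 14-day | 28-day |
|---|---|---|---|
| 1 | 3 | 6 | 12 |
| 2–3 | 2 | 5 | 11 |
| 4–5 | 1 | 4 | 10 |
| 6–7 | 0 | 3 | 9 |

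Hours per week = sessions × session length / weeks in the window.
- 7-day: scheduled time runs from 3.0–4.5 h on day 1 to 0 on days 6–7; active time from 2.0–4.0 h to 0.
- 14-day: scheduled time never falls below 3 × 60 / 2 = 90 min = 1.5 h; active time never below 3 × 40 / 2 = 60 min = 1.0 h.
- 28-day: scheduled time never falls below 9 × 60 / 4 = 135 min = 2.25 h; active time never below 9 × 40 / 4 = 90 min = 1.5 h.

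**Would it matter statistically? (illustration only)** Arm A analysed: 3 × 16 = 48. The probability that a spurious shift reaches two-sided 0.05 in a paired comparison is about Φ(shift × √48 / SD − 1.96). The documents give neither an alpha nor an SD of change, so SDs of 4, 6 and 8 h/week are assumed. A 2 h/week shift, the in-person active time at full overlap, gives 0.93, 0.64 and 0.41. A 1 h/week shift gives 0.41, 0.21 and 0.14.

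**Arm B.** Section 6.2 fills the 2 hours with exercise together with discussion, problem solving and a review of home safety, and gives no split. Active time could be anywhere from 0 to 2.0 h. Against 2.0 to 4.0 h in arm A, the A minus B difference at full overlap could be anything from 2.0 − 2.0 = 0 to 4.0 − 0 = 4.0 h.

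**The case against.** The strongest case on the other side limits the point in several ways.

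- A reader might infer that attendance alone would confirm the Aim 2 hypothesis. The documents do not support that. The hypothesis also names quality of life, measured by SF-36, and nothing links attendance to that score. Weekly steps are a second activity measure, and neither measure is ranked above the other.
- A reader might take 3.0 to 4.5 h/week as the size of the artefact. That is scheduled time including rest, and it is reached only at full overlap. In-person active time is about 2.0 h, below the entry limit, so it is not true throughout that the sessions equal or exceed the most activity an entrant could report.
- Subtracting arm B's 2 h to obtain an excess of 1.0 to 2.5 h for A over B is also unsupported, because arm B's active share is not stated.
- Session steps are recorded, so the protocol holds data from which session activity could be separated.
- This is a pilot, and section 12.0 does not include physical activity or quality of life in its ANCOVA list.

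All of this stands as a limit on size and reach. It does not remove the gap. No rule separates session steps from weekly steps or fixes the post-test step week, so steps are an independent check only if that window is free of sessions. The missing analysis plan for Aim 2 also means that nothing downstream corrects the questionnaire.

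**Conclusion.** The concern holds for the self-reported activity component of Aim 2. As written, the plan allows the intervention to be counted as a gain in activity in arm A's before-after comparison. The timing, the within-arm comparison and the absence of an exclusion rule are all in the documents.

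The size is conditional. With full overlap it is about 2.0 h/week of active time in person and 4.0 h/week online. With an assumed 7-day recall window it can fall to zero by the end of the post-test week; with an assumed 14 to 28 days it cannot. The recall window, the test day and the session days are assumptions. If the test day varies between participants, so may the bias. The contrast between arms may also be affected, but by an amount that cannot be stated.

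**What to change.** In section 6.4:

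1. State that at post-test, in both arms, the Physical Activity Scale for the Elderly is answered for activity outside study sessions and test visits. This works whatever the recall window, which should also be stated.
2. Take the before and after weekly step counts from weeks without sessions, or subtract the session steps already recorded.
3. Report session attendance, minutes and steps as training dose, not as a physical activity outcome.

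The differing in-person session lengths in sections 6.0 and 6.2 should be reconciled so that the dose can be reported.

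Postponing the questionnaire by a few days is not an adequate substitute: a 2 to 4 week recall window cannot be cleared within a one-week post-test.

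The cost is one instruction line on the questionnaire and a short rule for the step data. The downside is that some participants will find it harder to separate study activity from the rest, and the measured gain may be smaller.

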7.0 Expected Risks/Benefits

Potential Risks: Pertaining In-Person assessment and training

Reactive balance control: During the stance perturbation test, there is a slight risk of falls and injury (e.g., a muscle pull at shoulder or leg, muscle at the back).

Training sessions: As the training sessions involve high intensity training, the initial sessions may cause some muscle soreness in the lower limbs which may cause some discomfort during the first week of training, which will then be settled once the training sessions progress.

MRI scanning: The participants may experience discomfort as they are in an enclosed place with a loud noise generated during the MRI procedure. The participants will be given ear plugs to eliminate the MRI generated noise.

All participants will be monitored throughout the MRI scanning procedure through a camera while he/she is in the MRI scanner. They will be instructed that if any kind of discomfort is experienced to let us know immediately.

Preventing falls during the stance perturbation test (SPT) and limits of stability test (LOS): For both intentional and reactive balance control experiments, all the participants would be asked to wear a full-body protected harness to prevent any part of the body other than the feet contacting the treadmill belt (SPT)/force platform (LOS). The harness has adjustable shoulder and leg straps and will be attached to an overhead metal arch

that will allow the participants to perform movements freely having neither the knees nor hands from touching the treadmill belt/force platform. During the threat to balance control in stance position during the reactive balance control experiment, the safety harness will hold the participant and prevent him/her from falling. During the past several years, in more than 500 experimental sessions for both young and older adults conducted by the research team, similar harness systems have successfully protected Participants from injury following induced slips during standing or walking tasks. The harness system incorporates a number of safety features designed to limit the peak forces applied to the body, thereby minimizing the risk of injury upon a fall into the harness. The full-body harness is padded and provides support over a large contact area (>1500 cm²), primarily in regions that are able to withstand larger forces without injury (i.e. the pelvis and buttocks). Shoulder suspension of the harness provides protection against both forward and backward falls, with negligible risk of straps entanglement. Finally, the extent of body descent before harness assistance begins is limited (15 cm on average), very carefully calibrated and controlled. Our calculations indicate that, during a worst-case fall into the harness, an individual who weighs 1000 N would be Participated to a peak pressure of < 0.3 MPa, well below the stress threshold for even a moderate muscle contusion (1.9 MPa), requiring no medical treatment.

Preventing falls during training sessions: There is also a risk of balance loss and falls while participating in the actual balance training on the Wii-Fit balance board. For that reason, participants will always be made to wear gait belt and supervised by a research personnel mentioned in Appendix P during the training sessions. Blood pressure and heart rate will be monitored prior to the training session, after each sub-session (completion of 4 games). Participants will be given a chair to sit back after each subsession (completion of 4 games - approximately 10 minutes considering each game played for 1.5 minutes) or if he/she feels tired during the game (i.e., ≥ 15 on Borg scale for perceived exertion) or if the blood pressure is beyond normal limits (i.e. > 85% of age-predicted maximal heart rate). More than or equal to 15 on the Borg scale of perceived exertion indicates that the intensity of the physical activity performed was high and that it gives an idea to the research personnel that the participant would need to slow his movements down. Additionally, if at any point the heart rate, blood pressure, drops or rises above the pre-determined acceptable limits, the session will be terminated. Participants will be asked to inform the experimenter about any of the symptoms including marked breathlessness, excessive sweating, pain in chest, or fatigue. The research personnel will observe for any changes in participant's facial expression indicating anxiety or discomfort. In case of any discomfort, the session will be terminated, and the time of the training session will be noted.

Preventing injuries from training: The proposed setup incorporates several precautionary features, evolved through a decade of research, against such injuries. To further reduce the risk of injury, all Participants will undergo a series of stretching and warm-up exercises at the start of the experiment and training. A physical therapist or an exercise specialist on the team will conduct these procedures. Stretches will encompass all major muscle groups of the lower limbs and trunk. Warm-ups include activities such as walking, lunges, squats, high stepping and chair rise.

Potential Risks: Pertaining Online assessment and training

Clinical test related risks

- 1. The clinical balance tests performed pre-and post-intervention would present with a mild risk of losing balance while performing the activities. Subject would be remotely monitored by the research personnel and also asked to place a sturdy chair in front of them while performing these assessments.
- 2. The walking tests (2-minute step in place test and the training may be led to some amount of fatigue.
- 3. During the cognitive assessment which tests memory, attention, comprehension etc., participants may experience some disappointment if they are unable to perform a certain task.
- 4. The answering falls and physical activity questionnaire may have some questions about personal health information and daily physical activity habits and the subjects may be some discomfort while answering those questions.
- 5. During assessment and training sessions of Group 2 and 3, we will ask the "helper buddy" to note what the participant may be feeling. Incase of events like shortness of breath, excessive sweating, fatigue or muscle crams- the session will be stopped and the participant will be discontinued from the study

[figure not shown]

Figure 2: Adverse event protocol

Privacy related risk

Further, as all the tests will be performed in a home-based setting via online interface wherein the researcher personnel would be performing the assessments and training remotely, therefore at any point in time there is a potential for breach of privacy and confidentiality.

Potential Benefits:

Study participants will receive bone health status, balance performance from their osteoporosis screening and other physical ability tests. Such information can allow them to take any necessary preventive measures. In addition, this cognitive-motor exergaming is expected to promote significant benefits on reducing fall-risk by improving function of both the balance control and cognitive functions. Further, it delivers training via a low cost off-the shelf virtual gaming console for providing

repetitive, engaging and meaningful, task-orientated training. It also examines if the training-induced effects cause plasticity in the cognitive and motor control areas and networks in the brain. If participants demonstrate no gains, the training offered will maintain their optimal physical functioning and not result in any deterioration.

